9.1.3 Post-treatment (All Cohorts)

The Post-treatment Follow-up begins when the subject discontinues treatment. After subject discontinues treatment, an Off-Treatment Visit and the procedures noted in the Schedule of Assessments Tables ([Table 7](#), [Table 8](#), and [Table 9](#)) should be completed within 30 days after the last dose of drug. Subjects will be followed for survival every 3 months until death or for 1 year, whichever occurs first, unless the study is terminated or the subject discontinues due to withdrawal of consent or is lost to follow-up (see [Section 9.3.3](#)).

Subjects who discontinue treatment without disease progression will have tumor assessments performed every 6 or 8 weeks (per the appropriate tumor assessment schedule) for up to 1 year, or sooner if clinically indicated, for documented disease progression or until another anticancer therapy is initiated whichever occurs first. After data cutoff, tumor assessments may be performed as clinically indicated using the institutional guidelines, following the prevailing local standard of care.

As required by some regulatory agencies, the following estimates are provided:

- The study will begin in December 2014 and will end on or before December 2017.
- The maximum estimated period for the study is anticipated to be approximately 36 months. However, subjects will continue to receive study treatment as long as they demonstrate clinical benefit. Subjects benefiting from study treatment in the opinion of the investigator will continue to receive treatment until disease progression, intolerable toxicity, subject noncompliance with safety or efficacy assessments, initiation of another anticancer therapy, voluntary discontinuation by the subject at any time, or study termination by the sponsor, whichever occurs first.

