Treatment Phase: Tumor assessments of the chest, and other areas of known disease at Screening or newly suspected disease should be performed every 6 weeks (within Week 6) from C1D1 during the Treatment Phase (or sooner if there is evidence of progressive disease) and should utilize the same methodology (CT or MRI) and scan acquisition techniques (including use or nonuse of IV contrast) as was used for the screening assessments. Tumor response will be assessed according to RECIST 1.1. Subjects who discontinue must complete the off-treatment tumor assessment. Any CR or PR must be confirmed not less than 4 weeks following the initial achievement of the response. After treatment discontinuation, tumor assessment should continue to be performed every 6 weeks until documentation of progression for 1 year or start of a new anticancer agent (refer to [Section 9.5.1.3](#)).
- p. Brain CT with contrast or MRI pre- and post- gadolinium contrast will be performed at the Screening Visit, and as clinically indicated. For subjects with protocol-eligible treated brain metastases, brain CT/MRI will be performed at all tumor assessment time points.

- q. Height will be assessed at the Baseline Visit, Day 1 of every 3 cycles during the Treatment Phase, at the Off-treatment Visit and every 3 months during the Post-treatment Follow-up for 1 year. Proximal tibial growth plates x-rays should be conducted at baseline and at the Off-treatment Visit. Hand and wrist x-rays and tibial growth plate x-rays will be optional for Germany.
- r. Blood samples will be collected at the Baseline Visit, C1D8, Day 1 of all subsequent cycles, and at the Off-Treatment assessment for blood serum sample to measure factors implicated in angiogenesis. For subjects ongoing after the data cutoff data for the primary analysis, blood samples will be collected at the Off-Treatment Visit.
- s. An archival tumor sample from the most recent surgery or biopsy for identification of predictive biomarkers and pathology review may be collected at any time during the study, unless no such material is available.
- t. Collection of whole blood to obtain genomic DNA will be performed at the Baseline Visit. If sampling is not performed predose, sampling may occur at any subsequent visit in which other blood sampling is scheduled to occur. Pharmacogenetic markers of drug metabolism and drug transport may be assessed.

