5.1.2 Secondary Endpoints

- Efficacy endpoints:

- BOR over the treatment period (except for Cohort 2A): defined as the best response recorded from the start of study drug until 30 days after the last dose or until PD, whichever occurs earlier
- ORR (except for Cohort 2A): defined as the proportion of subjects who have BOR of CR or PR
- DOR: defined as the time from first documentation of tumor response (CR or PR) to PD
- Disease Control Rate (DCR): defined as the percentage of subjects with measurable disease who have a BOR of CR or PR or stable disease (SD) or subjects with evaluable disease who have a BOR of CR or Non-CR/Non-PD. To be assigned a BOR of SD or Non-CR/Non-PD, the time from the first administration of study drug until the date of documented SD or Non-CR/Non-PD should be ≥ 7 weeks
- Clinical Benefit Rate (CBR): defined as the percentage of subjects with measurable disease who have a BOR of CR or PR or durable SD lasting ≥ 23 weeks or subjects with evaluable disease who have a BOR of CR or durable Non-CR/Non-PD lasting ≥ 23 weeks
- TTP: defined as the time from the date of the first administration of study drug until the date of first documentation of PD.
- PFS: defined as the time from first dose to documented date of PD or death (whichever occurs first)
- Safety endpoints:
 - Adverse events (AEs), serious AEs (SAEs), clinical laboratory values, vital signs, 12-lead electrocardiograms (ECGs), urine dipstick, occult blood in stool, echocardiogram, Lansky play scores or Karnofsky performance status (KPS), physical examination findings, and height, and closure of proximal tibial growth plates during treatment and follow-up.
 - Plasma lenvatinib exposure parameters
 - Assessment of blood or tumor biomarkers that correlate with clinical response to lenvatinib treatment or AEs associated with lenvatinib treatment
 - Palatability and acceptability of the suspension formulation of lenvatinib

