5.4.2.2 Secondary Efficacy Analyses

The secondary efficacy endpoints include BOR over the treatment period (except for Cohort 2A), ORR (except for Cohort 2A), DCR, and CBR, as well as DOR (measurable disease only). PFS and TTP are defined in SAP [Section 5.1](#) and will be performed for subjects in the Full Analysis and Per Protocol Analysis Sets.

Subjects who do not have a tumor response assessment for any reason will be considered nonresponders and will be included in the denominator when calculating the response rate. The count and percentage for ORR will be summarized by dose level for Cohorts 1 and 3A and by cohort for Cohorts 2B and 3B. ORR and corresponding 95% CI based on the exact binomial distribution will be estimated for all corresponding treatment cohorts.

The count and percentage for both the DCR and CBR will be summarized for each treatment cohort, along with the exact 95% CI for.

The median and quartiles of DOR will be estimated by the Kaplan-Meier (KM) method ([Kaplan and Meier, 1958](#)), and the 95% CI estimated with a generalized Brookmeyer and Crowley method ([Brookmeyer and Crowley, 1982](#)).

For PFS, if a subject has not experienced PD or death, then the subject's data will be censored on the date of the last adequate radiologic assessment.

TTP will be calculated using data from all subjects in the Full Analysis Set. The calculation for TTP does not classify deaths as events.

The PFS censoring rules in this SAP and definition of progression date follow the [Food and Drug Administration \(FDA\), Guidance for Industry Clinical Trial Endpoints for the Approval of Cancer Drugs and Biologics \(2007\)](#) (See SAP Table 3). The PFS censoring rules are referenced in SAP Table 3 and TTP censoring rules are referenced in SAP Table 4.

Table 3 Censoring Rules for Analysis of Progression-Free Survival

No	Situation	Date of Progression or Censoring	Outcome
1	No baseline tumor assessments	Date of first dose	Censored
2	No postbaseline tumor assessments	Date of first dose	Censored
3	Progression documented between scheduled visits	Date of first radiologic PD assessment	Progressed
4	More than 1 NE tumor timepoint assessment	Date of last adequate radiologic assessment before NE tumor assessments	Censored
5	No progression at time of data cutoff	Date of last adequate radiologic assessment	Censored
6	New anticancer treatment started	Date of last adequate radiologic assessment prior to or on date of new anticancer treatment	Censored

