7	Death before first tumor assessment	Date of death	Progressed
8	Death between adequate assessment visits*	Date of death	Progressed
9	Death or progression after more than one missed visit/tumor assessment**	Date of last adequate radiologic assessment before missed tumor assessments	Censored
10	Treatment discontinuation for reasons other than PD	Date of last radiologic assessment before treatment discontinuation	Censored

CR = complete response, NE = not evaluable, PD = progressive disease, PR = partial response, q6w = every 6 weeks, q8w = every 8 weeks, SD =stable disease.

* Adequate tumor assessment is radiologic assessment at regular interval as defined in the protocol.

** More than 1 missed visit/adequate tumor assessment is defined as having either 1 of the following 2 durations being longer than 18 weeks – 1 day, which is 125 days ($= ((8+1) \times 2 \times 7) - 1$) for subjects on the q8w tumor assessment schedule in Cohorts 1, 2A and 2B; while 14 weeks – 1 day, which is 97

days (= ((6+1) x 2 x 7) – 1) for subjects on the q6w tumor assessment schedule in Cohorts 3A and 3B:

- a. Duration between 2 consecutive tumor assessments
- b. Duration between the last adequate tumor assessment and death or PD

The priority of the censoring rules is as follows:

1. If the subject had PD or death, the following sequence will be applied:

- If a subject did not have a baseline or postbaseline tumor assessment (Nos. 1 and 2), the subject will be censored on the date of first dose. However, if the subject died within 125 days in Cohorts 1, 2A and 2B or 97 days in Cohorts 3A and 3B following the first dose and did not receive a new anticancer treatment, it will be counted as PFS event at the date of death. If a subject had new anticancer treatment before PD or death (No. 6), the subject will be censored on the date of the last adequate tumor assessment prior to or on the date of new anticancer treatment. If PD is reported after the drug discontinuation visit, the subject will be censored at the date of last radiologic assessment before drug discontinuation except when PD happened at the same visit as drug discontinuation (No. 10). If PD happened within 4 weeks of drug discontinuation (Week 16 for Cohort 2 and Week 18 for Cohorts 3A and 3B), it will be considered PD at drug discontinuation visit and counted as PFS event.

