- b. Duration between the last adequate tumor assessment and PD

The priority of the censoring rules is as follows:

1. If the subject had PD, the following sequence will be applied:
 - If a subject did not have a baseline or postbaseline tumor assessment (Nos. 1 and 2), the subject will be censored on the date of first dose. If a subject had new anticancer treatment before PD (No. 6), the subject will be censored on the date of the last adequate tumor assessment prior to or on the date of new anticancer treatment. If PD is reported after the drug discontinuation visit, the subject will be censored at the date of last radiologic assessment before drug discontinuation except when PD happened at the same visit as drug discontinuation (No. 8). If PD happened within 4 weeks of drug discontinuation (Week 16 for Cohort 2 and Week 18 for Cohorts 3A and 3B), it will be censored at drug discontinuation visit.
 - If a subject died before first tumor assessment (No. 7) or died between adequate assessment visits (No. 8), the subject will be censored on the date of death.
 - If a subject missed 2 or more tumor assessments before PD or death (No. 9), the subject will be censored on the date of the last adequate tumor assessment before PD or death. Note that if a subject is censored by both this criterion and the anticancer treatment criterion, the earliest censoring date will be used.
 - Otherwise, if a subject had an event (No. 3), the earliest event date will be used.
2. If a subject did not have PD, the censoring date will be the earliest censoring date if the subject met multiple censoring criteria (No. 1, No. 2, No. 4, No. 5, No. 6, No 9).

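### Progression found within 4 weeks of stopping drug is an event in PFS but is censored in TTP, against the SAP's own TTP definition

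*SAP*

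**What the plan says.** SAP 5.1.2 defines TTP as the "time from the date of the first administration of study drug until the date of first documentation of PD". SAP 5.4.2.2 then states how TTP departs from PFS: "The calculation for TTP does not classify deaths as events". It names no other departure.

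The priority text below each censoring table covers progression found within 4 weeks of stopping drug, with the same parenthesis about Week 16 and Week 18 in both places:

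- PFS (Table 3): "it will be considered PD at drug discontinuation visit and counted as PFS event".
- TTP (Table 4), where the sentence ends: "discontinuation (Week 16 for Cohort 2 and Week 18 for Cohorts 3A and 3B), it will be censored at drug discontinuation visit".

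The sentence just before it in each text censors progression reported after the discontinuation visit. The PFS text ties this to row 10 (treatment discontinuation for reasons other than progression). The TTP text ties it to row 8, which in Table 4 is death between adequate assessments.

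SAP section 7, which lists changes in the planned analyses, does not mention a different treatment of progression in TTP.

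**The concern.** A progression in this window is not a death, so the one stated difference between the endpoints cannot explain why they treat it in opposite ways. The wording also suggests a drafting slip. In the PFS text the 4-week sentence is an exception that rescues an event the previous sentence would have censored. In the TTP text it rescues nothing. It only moves the censoring date from the last scan before discontinuation to the discontinuation visit. The wrong row number in the same bullet points the same way.

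In a cohort with no deaths before progression, the PFS and TTP curves should coincide. As written, they separate whenever a progression falls in the window, and a reader would attribute the gap to deaths. The quantities affected are the TTP quartiles, the 4- and 12-month TTP rates (reported when enough subjects remain at risk), and the reverse Kaplan-Meier follow-up for TTP, where each such progression would count as completed follow-up.

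**Working it through.** The plan gives no figure for this point, so there is none to reproduce.

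**Can the situation arise?** Protocol 9.3.3 keeps subjects who stop without progression on scans every 6 or 8 weeks. Under Protocol 9.1.3 the Off-Treatment Visit procedures "should be completed within 30 days after the last dose of drug". For Cohorts 3A and 3B the notes to Protocol Table 9 add: "Subjects who discontinue must complete the off-treatment tumor assessment". A scan can therefore fall up to 4 weeks after stopping. The SAP does not define the drug discontinuation visit. If it is the Off-Treatment Visit, progression found there meets the same-visit exception and stays an event in both analyses. If not, it falls in the window.

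**Direction.** Both rules use the same date, so the subject leaves the risk set at the same time and all later factors are equal. With n at risk on that date and no tie, the event contributes (1 - 1/n) under PFS and the censored record contributes 1 under TTP. Hence TTP estimate = PFS estimate × n/(n-1) from then on; for k such cases with no other event between them the factor is n/(n-k). It is never below 1.

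**Worked example** (assumed data): 27 subjects, no deaths, scans at days 56 and 112, 13 progressions by the first scan, 7 more by the second, 7 progression-free. Recoded cases are dated at drug stop.

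| Progressions in window | Drug stopped | PFS rule | TTP rule |
|---|---|---|---|
| 0 | - | 7/27 = 25.9% | 7/27 = 25.9% |
| 1 | before day 56 | 25.9% | 7/27 × 27/26 = 7/26 = 26.9% |
| 1 | between scans | 25.9% | 7/27 × 14/13 = 27.9% |
| 2 | before day 56 | 25.9% | 7/27 × 27/25 = 7/25 = 28.0% |
| 2 | between scans | 25.9% | 7/27 × 14/12 = 30.2% |

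**Simulation** (all inputs assumed): 400,000 subjects per setting; constant on-drug hazard leaving 25% progression-free at day 112; uniform stop times; progression detected at 8-weekly scans; hazard after stopping 0.5, 1, 2 or 3 times the on-drug hazard.

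| Stop drug early | Share of progressions in window | TTP minus PFS, 4-month rate |
|---|---|---|
| 10% | 2.3-3.2% | 0.6-0.9 points |
| 20% | 4.7-6.2% | 1.3-1.8 points |
| 30% | 7.1-9.1% | 2.1-2.9 points |

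The sign is the same in all 12 settings. If everyone who stops also has an off-treatment scan 0-28 days later that is not treated as the discontinuation visit, the window holds 3.5-16.1% of progressions and the gap is 0.9-4.8 points.

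**The case against.** TTP is a secondary endpoint, described by Kaplan-Meier without a test, and no decision in the trial depends on it. The effect is small against the precision available: for 7/27 the Greenwood log-log interval is about 11-43% at 95% and 16-37% at 80%. The simulated gaps rest on stopping rates and hazards that the documents do not give, and on applying the 4-week rule to any stop. If the parenthesis confines the rule to stops around Week 16 or 18, or if new anticancer treatment begins soon after stopping (row 6 of both tables), fewer progressions qualify. If the Off-Treatment Visit is the discontinuation visit, a separate scan inside 4 weeks would be needed, which is uncommon on a 6- or 8-week schedule. Finally, matching TTP to PFS restores symmetry but not the literal definition: the event would be dated at the discontinuation visit rather than at the scan, and row 10 would still censor later off-drug progression.

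All of this limits the size and importance of the point, and it is why the figures above are illustrations only. None of it reconciles the two sentences or supplies a reason for the difference. The dating rule and row 10 are common to both endpoints and so do not cause the asymmetry.

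**Conclusion.** The concern holds. As written, the TTP rule contradicts the TTP definition and the statement that only deaths are handled differently. The direction is certain: TTP reads at or above PFS for a reason unrelated to deaths. The size is not known. It is 1 to 4 points for one or two affected subjects in the assumed cohort of 27, and 0.6-2.9 points in the main simulation. These figures measure the gap between the two written rules and are not a claim of bias against the true rate. The primary PFS-4 test and the Cohort 2B two-stage rule do not use TTP and are unaffected. The correction should be made, but it does not threaten the trial's main conclusions.

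**What to change.** In the Table 4 priority text, replace the censoring outcome for progression within 4 weeks of stopping drug with the outcome used for PFS, reading TTP event for PFS event. In the sentence before it, change the row reference from No. 8 to No. 10. If the difference is intended, state it and give the reason.

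Three clarifications are worth making in both texts at the same time: whether the Week 16/18 parenthesis limits the rule to progression before that landmark, what applies to Cohort 1 (which it does not name), and what counts as the drug discontinuation visit. Row 10 and the PFS dating rule can stay. A labelled sensitivity analysis for both endpoints, counting all radiologic progression before new anticancer therapy on its scan date, is optional and would answer the dating objection.

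The cost is a few sentences of SAP text and one programming line, with no new data. The reported TTP rate falls slightly if any progression lies in the window.

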5.4.3 Other Efficacy Analyses

5.4.3.1 Exploratory Efficacy Analyses

OS

OS is measured from the start date of the treatment period until date of death from any cause. All events of death will be included, regardless of whether the event occurred while the subject was still taking study drug, or after the subject discontinued study drug. If a subject has no record of death, then the data will be censored at the date the subject was last known to be alive, or the data cutoff date, whichever is earlier (censoring rules see SAP Table 5). The distribution of OS will be estimated using the KM method. Median, Q1 and Q2 survival times will be estimated by KM method, and the 95% confidence interval estimated with the Brookmeyer and Crowley method. Survival rates at 4 and 12 months will be estimated using the KM method (and corresponding 95% CIs estimated with the Greenwood formula using the log-log transformation) for each treatment cohort when an adequate number of at-risk subjects at those time points warrant the estimate. Follow-up time for OS will be presented KM method. Median, Q1, and Q2 follow-up times, and the 95% CIs (using the Brookmeyer and Crowley method) will be estimated. Estimates for OS follow-up time are calculated in the same way as the KM estimate of OS, but with the meaning of ‘censor’ and ‘event’ status indicator reversed.

Table 5 Censoring Rules for Overall Survival Endpoint

Situation	End Date	Outcome
Death during study	Date of death	Death
Death after data cut-off	Date of data cut-off	Censored event
Subject still alive at data cut-off	Date of data cut-off	Censored event
Subject lost to follow-up before data cut-off	Date last known to be alive	Censored event

PFS-4 RATE FOR COHORT 3A

This analysis will be performed for Cohort 3A. See [Section 5.4.2.1 cohort 3B: osteosarcoma combination expansion](#) for details.

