3.3.5 Post-treatment (All Cohorts)

The Post-treatment Follow-up begins when the subject discontinues treatment. After subject discontinues treatment, an Off-Treatment Visit and the procedures noted in the Schedule of Assessments Tables (see Protocol Table 7, Table 8, and Table 9) should be completed within 30 days after the last dose of drug. Subjects will be followed for survival every 3 months until death or for 1 year, whichever occurs first, unless the study is terminated or the subject discontinues due to withdrawal of consent or is lost to follow-up (see Protocol Section 9.3.3).

Subjects who discontinue treatment without disease progression will have tumor assessments performed every 6 or 8 weeks (per the appropriate tumor assessment schedule) for up to 1 year, or sooner if clinically indicated, for documented disease progression or until another anticancer therapy is initiated whichever occurs first. After data cutoff, tumor assessments may be performed as clinically indicated using the institutional guidelines, following the prevailing local standard of care.

As required by some regulatory agencies, the following estimates are provided:

- The study will begin in December 2014 and will end on or before December 2017 (revised estimate is April 202).
- The maximum estimated period for the study is anticipated to be approximately 36 months. However, subjects will continue to receive study treatment as long as they demonstrate clinical benefit. Subjects benefiting from study treatment in the opinion of the investigator will continue to receive treatment until disease progression, intolerable toxicity, subject noncompliance with safety or efficacy assessments, initiation of another anticancer therapy, voluntary discontinuation by the subject at any time, or study termination by the sponsor, whichever occurs first.

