5 STATISTICAL METHODS

All descriptive statistics for continuous variables will be reported using n, mean, SD, median, 25th percentile (Q1), 75th percentile (Q3), minimum and maximum. Categorical variables will be summarized as number (percentage) of subjects. The statistical analyses of the study data as described in this section will be performed as further outlined in this SAP, which will be finalized before database lock and be included in the CSR.

Efficacy will be evaluated based on the Full Analysis Set (see SAP [Sections 5.2.1](#) and [7.2](#)). Each cohort will have its own cutoff date for the final analysis for CSR reporting purposes. For Cohorts 1 and 3A, the data cutoff will occur when the RD is determined and the last enrolled subject completes 6 cycles of treatment or discontinues before the end of Cycle 6, whichever occurs first or pending discussion with the PSC. For DTC and osteosarcoma subjects in Cohorts 2A, 2B, and 3B, the cutoff will be after all subjects enrolled have either completed 6 cycles or have discontinued treatment before the end of Cycle 6, whichever occurs first.

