5.1.3 Exploratory Endpoints

- Time to OS: defined as the time from first dose of study drug until the date of death from any cause. Subjects who are lost to follow-up and those who are alive at the date of data cutoff will be censored at the date the subject was last known to be alive (or the data cutoff date).
- PFS-4 in Cohort 3A (see SAP [Section 7.1](#)).

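### SAP Table 5 on overall survival can conflict with the text it sits under: it has no correct row for subjects who finished the 1-year survival follow-up or withdrew consent before data cut-off

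*SAP*

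**What the plan says.** The text of SAP 5.4.3.1 says that a subject without a recorded death is "censored at the date the subject was last known to be alive, or the data cutoff date, whichever is earlier", and it points to Table 5 for the censoring rules. SAP 5.1.3 and the OS definition in Protocol 9.7.1.1 apply the last-known-alive date to living subjects as well as lost ones: "those who are alive at the date of data cutoff will be censored at the date the subject was last known to be alive", with the cut-off date added in brackets. SAP 8.3.5 defines how that date is derived.

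Table 5 divides subjects differently. "Subject still alive at data cut-off" is given the cut-off date, with no condition on when the subject was last contacted. Last known alive appears in one row only, "Subject lost to follow-up before data cut-off".

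Three other places determine who falls between these rows:

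- **Contact schedule (SAP 3.3.5, Protocol 9.1.3):** "Subjects will be followed for survival every 3 months until death or for 1 year, whichever occurs first". The year starts at the end of treatment: "The Post-treatment Follow-up begins when the subject discontinues treatment".
- **Cut-off for Cohorts 2A, 2B and 3B (SAP 5):** "the cutoff will be after all subjects enrolled have either completed 6 cycles", or have stopped treatment before then.
- **Withdrawal (Protocol 9.5.5):** loss to follow-up and withdrawal of consent are separate discontinuation reasons, and no data are collected after consent is withdrawn.

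**The concern.** Cut-off waits for the last subject enrolled, so early enrolees can finish their year of survival contact well before it. Such a subject is neither lost nor confirmed alive at cut-off. The same holds for a subject who withdrew consent. In Table 5 the nearest row is the one for living subjects, and that row counts all time to cut-off as observed and event-free. A death after the last contact that nobody reports would be counted as survival.

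Two programmers could therefore build different OS datasets from one section. The outputs at stake are the OS curve after 12 months and the OS follow-up time. The SAP plans the latter by reversing event and censoring in the Kaplan-Meier estimate, so it depends directly on the censoring dates.

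**Working it through.** The plan states no assumed rate, event count or power for OS, so there is no figure to reproduce.

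**1. Where the rules differ**

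| Subject with no death record | Text of 5.4.3.1 | Table 5 |
|---|---|---|
| Confirmed alive at or after cut-off | cut-off (the earlier date) | cut-off |
| Lost to follow-up before cut-off | last known alive | last known alive |
| Completed 1-year follow-up before cut-off | last known alive | no row; cut-off if coded as still alive |
| Withdrew consent before cut-off | last known alive | no row; cut-off if coded as still alive |

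**2. Inputs**

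From the documents: survival contact for 12 months after treatment ends, and cut-off six cycles after the last enrolment. Six cycles are 6 × 28 = 168 days (168/30.4375 = 5.5 months) for single agent, and 6 × 21 = 126 days (4.1 months) for the combination.

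Assumed, because the documents do not give them: exponential OS with median m = 6, 12 or 24 months; exponential treatment duration with median τ = 3 or 6 months; uniform accrual over A = 12, 24 or 36 months. Table 5 is read as: no death record and not lost means cut-off date. Status is taken as known at cut-off for anyone still in follow-up.

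**3. OS curve, 1-year completers only**

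The year runs from the end of treatment, so every completer has been observed for at least 12 months from first dose. Up to 12 months the two rules give the same curve.

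After that, Table 5 records a death at month 12+s only if treatment lasted longer than s. This gives

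S_T5(12+s) = 2^(−12/m) × [1 − k(1 − 2^(−s(1/m + 1/τ)))], with k = τ/(m+τ).

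The true value, which the text rule estimates, is 2^(−(12+s)/m).

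For m = 12 and τ = 3, k = 3/15 = 0.2:

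- 18 months: 0.5 × [1 − 0.2(1 − 2^(−2.5))] = 41.8%, against 2^(−1.5) = 35.4%.
- 24 months: 0.5 × [1 − 0.2(1 − 2^(−5))] = 40.3%, against 25.0%.

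| m, τ (months) | 18-month OS: true, Table 5, gap | 24-month OS: true, Table 5, gap |
|---|---|---|
| 6, 3 | 12.5, 17.7, +5.2 | 6.2, 16.8, +10.5 |
| 6, 6 | 12.5, 15.6, +3.1 | 6.2, 13.3, +7.0 |
| 12, 3 | 35.4, 41.8, +6.4 | 25.0, 40.3, +15.3 |
| 12, 6 | 35.4, 39.2, +3.9 | 25.0, 35.4, +10.4 |
| 24, 3 | 59.5, 64.5, +5.0 | 50.0, 63.2, +13.2 |
| 24, 6 | 59.5, 62.5, +3.1 | 50.0, 59.1, +9.1 |

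Simulation with 200,000 subjects per scenario and 24 or 36 months of accrual gave gaps between the two rules of +3.0 to +6.5 points at 18 months and +6.8 to +15.6 at 24 months. The median OS moves only if it lies beyond 12 months; an assumed median of 24 months becomes not reached.

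With 12 months of accrual the longest follow-up is 12 + 4.1 = 16.1 or 12 + 5.5 = 17.5 months, so 18- and 24-month rates could not be estimated.

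**4. Median OS follow-up**

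Under Table 5 it is the median time from entry to cut-off, A/2 + 4.1 or A/2 + 5.5. Under the text rule it solves [(A + lag − t)/A] × 2^(−(t−12)/τ) = 0.5 when t exceeds 12, where lag is 4.1 or 5.5.

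| Accrual | Text rule | Table 5 |
|---|---|---|
| 12 months | 10.1 to 11.5 | 10.1 to 11.5 |
| 24 months | 13.0 to 14.1 | 16.1 to 17.5 |
| 36 months | 13.7 to 15.3 | 22.1 to 23.5 |

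**5. What could move the 12-month rate**

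- **Early withdrawal.** Assume 10% withdraw, uniformly over months 0 to 6, and are carried to cut-off. The 12-month rate rises by 0.1 × [mean of S over months 0 to 6 − S(12)]. For m = 10 this is 0.1 × (0.818 − 0.435) = 3.8 points; for m = 12 it is 0.1 × (0.845 − 0.500) = 3.5 points.
- **Status known only at the last 3-monthly contact.** The simulation gave +0.5 to +5.0 points at 12 months and at most +0.4 at 4 months.

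**The case against.** The strongest reply is that the SAP already contains the right rule. The sentence in 5.4.3.1 covers every subject without a death record, 5.1.3 points the same way, and 8.3.5 defines the date. For a subject truly known to be alive at cut-off, the earlier of the two dates is the cut-off, so the row and the sentence agree. An error arises only if a programmer codes a subject of unknown status as still alive, which the SAP does not instruct. That is correct, and it narrows the point. It does not remove it, because the sentence names Table 5 as the source of the rules and the table has no other row for these subjects.

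A reader might go further and infer three things that the documents do not support.

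- **That OS will be overstated.** This depends on how the living-subject row is applied, on whether status is updated at cut-off, and on each cohort's accrual length. The documents give none of these. The text also says that all deaths are included, so a later death that becomes known would count. Protocol 9.5.5 speaks of survival follow-up after discontinuation without repeating the 1-year limit.
- **That the planned rates are biased by completed follow-up.** They are set at 4 and 12 months, and completers cannot affect either.
- **That a 1-point difference between the rules at 12 months shows Table 5 running high.** In a simulated example with median OS 10 months, Table 5 gave 43.3% and the last-known-alive rule 42.0%. The assumed truth is 2^(−1.2) = 43.5%, so most of that gap is the comparator running low.

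Finally, with 30 subjects and OS near 42%, the standard error is √(0.42 × 0.58/30), about 9 points. No test, sample size or decision rests on OS.

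**Conclusion.** Wrong as written, with low severity. The two rules in SAP 5.4.3.1 can give different censoring dates, and Table 5 has no correct row for completed survival follow-up or withdrawn consent.

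The inflation is conditional on coding these subjects as still alive. For 1-year completers it then affects follow-up time and the curve beyond 12 months by the amounts given above, under exponential survival and 24 to 36 months of accrual. With 12 months of accrual median follow-up is unchanged. The 4- and 12-month rates are safe from completers, though the 12-month rate is not safe from early withdrawals or from status known only at the last contact.

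OS is a secondary objective in Protocol 8.2 but exploratory in SAP 3.2 and 5.1.3, and it is reported descriptively. No primary conclusion depends on it.

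**What to change.** Replace the third and fourth rows of Table 5 with one row:

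- Situation: no record of death, including completed survival follow-up, withdrawn consent and loss to follow-up.
- End date: the earlier of the last known alive date (SAP 8.3.5) and data cut-off.
- Outcome: censored.

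Add one sentence stating whether survival status is updated at cut-off for all subjects, including those whose year of contact has ended.

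The row change needs no new data, since it matches the rule already in the text, and it can be made before database lock. The added sentence only has to state what will be done; an actual status update at cut-off would mean extra site contact, but the corrected rule works without one.
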